### *Sample Size Calculation*

Necessary number of patients was estimated considering a normal distribution means two proportions formula, using  $\alpha = 0.05$  (two tails),  $\beta = 0.20$ , 1 on 1 proportion of assignment to each group. For calculus it was considered that non-exposed group will have a proportion of 62%, while supplemented group will have a proportion of 42% (delta

20%). With the previous conditions and considering a continuity correction, to perform the study it is required to randomize 214 cycles and assign 107 to control group and 107 to supplemented group. Calculus was done with Sample Size Calculator for Designing Clinical Research by University of California San Francisco, available at <http://www.sample-size.net/sample-size-proportions/>.

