### **Cisplatin-induced hypomagnesemia**

Cisplatin is one of the most nephrotoxic drug used in clinical setting. Cisplatin-induced hypomagnesemia has an origin in the direct damage on magnesium reabsorption mechanisms at Henle's loop and distal tubule. The incidence of hypomagnesemia in children that receive cisplatin is around 40%.

Due to the importance of maintenance of adequate magnesium levels different strategies have been proposed. Studies done on guinea pigs have shown that a rich magnesium diet can prevent severe cisplatin-induced hypomagnesemia.

Most of clinical studies conducted on this manner have focused on intravenous administration of magnesium to prevent and treat cisplatin-induced hypomagnesemia. Nevertheless, there is evidence showing that oral supplementation with magnesium salts can be effective to prevent hypomagnesemia. Willox et al., reported that oral supplementation

with magnesium citrate, between chemotherapy cycles in patients with testicular cancer receiving cisplatin, increases significantly magnesium concentration in comparative with a group of patients that didn't receive the supplement. Martin et al., demonstrated that prophylactic oral supplementation with magnesium pidolate reduced in 50% the episodes of hypomagnesemia in patients treated with four cycles of cisplatin. In Iran, oral supplementation with magnesium oxide reduced in 13% the prevalence of hypomagnesemia in adult patients with cancer treated with cisplatin.

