### **Magnesium's role in infectious process**

Magnesium plays an important role on immune response in different ways: it is a necessary cofactor for immunoglobulin and C3 convertase synthesis, it participates in immune cell adherence, antibody-dependent cytolysis, lymphocytes union, macrophage response to lymphokines, adherence between T lymphocytes and B lymphocytes, adherence of P substance to lymphoblast, and antigen to RNA binding of macrophages.

Low serum concentration of magnesium had been associated with acute bacterial infections, although low association had been made with viral acute infections. In the same sense, hypomagnesemia has been associated with development of sepsis in critically ill patients at Intensive Care Units. Moreover, it has been demonstrated that low intake of magnesium in the diet alters the morphology and the immune response of gut mucosae in mice.

Recently, our team has reported an independent association between hypomagnesemia and FN in pediatric patients with solid tumors treated with cisplatin-based chemotherapy (RR = 8.20, CI95% [1.81-37.14]). This evidence suggests that if reduction of serum concentrations of magnesium is prevented, the incidence of FN can be diminished. Supporting this hypothesis, Willox et al., showed that supplementation with magnesium

citrate presents a tendency to reduce FN episodes (about 15%) in adult patients with testicular cancer treated with cisplatin. However, the small number of patients included in the study, and the fact that the study wasn't designing to prove reduction of apparition of FN limited the statistical power of these findings.

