### **3. Problem statement**

Febrile Neutropenia (FN) is an important and serious health problem in children that receive chemotherapy because it increments the risk of major complications, it reduces the patient's quality of life, and increments treatment costs. Moreover, it is the most common diagnosis in children with cancer admitted into emergency rooms and the second cause of hospitalization, just after hospitalization for chemotherapy. In Mexico, FN incidence is 62% in children with solid tumors treated with cisplatin-based chemotherapy (CBC). Cisplatin is one of the most nephrotoxic drugs used in the clinic, this nephrotoxicity is showed by tubular damage that has electrolyte losses as a consequence, specially magnesium loss. Recently, an association between hypomagnesemia and the apparition of FN has been demonstrated. This finding can be explained based on the participation of magnesium as a cofactor in immune responses. Previous clinical trials, made in adult population, have showed that oral supplementation with magnesium in between chemotherapy cycles increment the serum concentration of magnesium and reduce hypomagnesemia episodes. With these evidences put together, we hypothesize that oral supplementation with magnesium oxide in between CBC cycles in children with solid tumors will maintain serum concentrations of magnesium in physiological parameters and in consequence this electrolyte will exercise its function in the immune system, contributing to the reduction of FN episodes. Therefore, the purpose of this protocol is to determine the efficacy of oral supplementation with magnesium to reduce incidence of febrile neutropenia in pediatric patients treated with cisplatin-based chemotherapy.

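### Is the 20-point fall in febrile neutropenia that sizes the trial larger than the protocol's own magnesium figures allow?

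*Combined protocol and SAP*

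**What the plan says.** The Sample Size Calculation takes two-sided alpha 0.05, beta 0.20, 1:1 allocation and a continuity correction. It assumes that the "non-exposed group will have a proportion of 62%, while supplemented group will have a proportion of 42" per cent, and arrives at 107 cycles per arm. Two references support these rates: the team's own risk-factor study in children (also the source of the 62%) and the adult magnesium oxide trial.

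The Background supplies the figures that might lie behind the 20 points:

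- On hypomagnesemia in children: "The incidence of hypomagnesemia in children that receive cisplatin is around 40" per cent.
- On the magnesium oxide trial: "oral supplementation with magnesium oxide reduced in 13% the prevalence of hypomagnesemia in adult patients".
- On the magnesium pidolate trial: it "reduced in 50% the episodes of hypomagnesemia in patients treated with four cycles of cisplatin".
- On the link between hypomagnesemia and FN, from the risk-factor study: "RR = 8.20, CI95% [1.81-37.14".
- On FN directly, from a small adult trial: magnesium "citrate presents a tendency to reduce FN episodes (about 15%) in adult patients with testicular cancer treated with cisplatin".

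On the mechanism, the Background reasons that "if reduction of serum concentrations of magnesium is prevented, the incidence of FN can be diminished". The Problem statement expects that supplementation "will maintain serum concentrations of magnesium in physiological parameters and in consequence this electrolyte will exercise its function in the immune system". The Hypothesis section then goes from a 13 to 50% reduction in hypomagnesemia to a 20% reduction in FN, with no calculation between them.

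**The concern.** If magnesium lowers FN only by preventing hypomagnesemia, the fall in FN cannot exceed the fall in hypomagnesemia. The oxide trial cited for the sample size is credited with 13%, so on that route it cannot support 20 points. The more favourable pidolate figure also seems to fall short once it is combined with the 40% and 62%.

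At stake is power. If the true effect is nearer 13 points, 107 per arm has less than an even chance of a relative-risk interval that excludes 1, which is the criterion in the Analysis data plan. A non-significant result might then be taken for absence of effect from a trial with 80% power.

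**Working it through.** **1. The plan's own figure.** With p1 = 0.62, p2 = 0.42, d = 0.20 and mean rate 0.52:

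- Uncorrected n = [1.960 × √(2 × 0.52 × 0.48) + 0.842 × √(0.62 × 0.38 + 0.42 × 0.58)]² / 0.20² = (1.385 + 0.583)² / 0.04 = 96.8.
- Continuity-corrected n = (96.8 / 4) × [1 + √(1 + 4 / (96.8 × 0.20))]² = 106.5, which rounds up to 107.

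The stated size reproduces exactly. Power at 107 per arm is 80% corrected and 84% uncorrected.

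**2. The mechanism bound.** Let h be the rate of hypomagnesemia without supplementation, F the FN rate, a and b the FN risks with and without hypomagnesemia, and Δ the absolute fall in hypomagnesemia. Then

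fall in FN = Δ × (a − b), with h·a + (1 − h)·b = F.

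With h = 0.40 and F = 0.62, a − b is largest at a = 1, where b = (0.62 − 0.40) / 0.60 = 0.367 and a − b = 0.633.

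| Fall in hypomagnesemia | Δ | Largest fall in FN |
|---|---|---|
| 13%, relative | 0.052 | 3.3 points |
| 13%, percentage points | 0.13 | 8.2 points |
| 50%, relative | 0.20 | 12.7 points |
| 50%, percentage points (capped at all 40) | 0.40 | 25.3 points |

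A 13-point fall in FN from the oxide figure needs a = 1 and b = 0. That forces h = F = 62%, which is not the 40% in the Background.

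**3. Do the inputs agree with each other?** With h = 0.40 and F = 0.62, a risk ratio of 8.20 gives b = 0.62 / (0.60 + 0.40 × 8.20) = 0.160 and a = 8.20 × 0.160 = 1.31, which is impossible. One of the three figures must give way.

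- Keep 40% and 62%, and read 8.20 as an odds ratio: a = 0.871, b = 0.452, and a 50% relative fall gives 0.20 × 0.419 = 8.4 points.
- Keep 62% and the risk ratio: a ≤ 1 requires b ≤ 1 / 8.20 = 0.122, so h ≥ (0.62 − 0.122) / (1 − 0.122) = 57%. A 50% relative fall then gives 0.5 × (0.62 − 0.122) = 24.9 points.

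**4. Sensitivity to h.** For a 50% relative fall the ceiling is 0.5 × h × (1 − F) / (1 − h). This is 8.1 points at h = 30%, 12.7 at 40% and 19.0 at 50%; it passes 20 just above 51%.

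**5. Power at 107 per arm, 62% control rate.**

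| Fall in FN | Corrected | Uncorrected |
|---|---|---|
| 20 points | 80% | 84% |
| 15 points | 54% | 60% |
| 13 points | 43% | 48% |
| 12.7 points | 41% | 46% |
| 8.2 points | 19% | 23% |

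At 13 points the expected relative risk is 0.49 / 0.62 = 0.79, with 95% interval 0.62 to 1.01.

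**The case for a change.** The strongest case for a change is this. The oxide trial tested the salt used here, and its 13% cannot give 20 points through prevention of hypomagnesemia under any reading. The two readings that reach 25 points are strained: a 50-point fall cannot come out of 40%, and a true risk ratio of 8.20 needs at least 57% hypomagnesemia, which no section reports. The one direct FN figure is about 15%. A sentence justifying the difference, with power at smaller effects, would cost no patients.

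Part of this stands. The 20 points is not derived, the oxide trial's 13% does not carry it on this route, and power drops quickly for smaller effects.

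It does not establish that 20 points is wrong:

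- The 12.7 depends on choosing the 40% over the risk ratio. The risk ratio comes from the same study as the 62%; the 40% comes from a separate review of renal effects.
- The Hypothesis section words its 20% reduction in the same way as the 13% and 50%, and there the sample size shows it to be absolute. An absolute reading of the 50% therefore cannot be excluded.
- The bound counts benefit only when a cycle is kept from crossing the hypomagnesemia threshold. The Background and Problem statement speak of maintaining concentrations and immune function, and Appendix 3 also treats serum magnesium as continuous. Smaller changes in level could matter.
- The 15% is a tendency in a small adult trial that was not designed for FN. It is 15 points if absolute and 0.15 × 62 = 9.3 points if relative.

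**Conclusion.** No change to the plan is needed. The 20 points is presented as a hypothesis. The trial is correctly sized for it, and the documents neither derive it nor rule it out: depending on which of three incompatible figures is kept, and on whether the 50% is relative or absolute, the most favourable cited reduction in hypomagnesemia allows roughly 8 to 25 points.

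Enrolling more cycles would mean sizing on a smaller effect that is no better supported than the present one. Tabulating power at other differences would leave the design and the analysis as they are. The Analysis data plan already gives the relative risk with its 95% interval, the absolute risk reduction and the number needed to treat. It says only when a relative risk counts as significant, and nowhere equates a non-significant result with lack of efficacy. An interval such as 0.62 to 1.01 shows its own uncertainty. The planned hypomagnesemia comparison will show whether magnesium status changed.

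This rests on applying the 40% and 62%, reported for children, to cycles, and on treating cycles as independent with no losses in the power figures. The non-inclusion of patients already hypomagnesemic before chemotherapy adds further doubt about the 40%, so it is a weak basis for a firm ceiling.

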## 1. Abstract

**Background.** Febrile neutropenia (FN) is a worrying outcome in children receiving chemotherapy because it increments the risk of major complications, reduces quality of life and increments treatment costs. Moreover, it is the most common diagnosis in pediatric oncology patients admitted into emergency rooms and represents the second cause of hospitalization, just behind hospitalization for administration of chemotherapy.

**Problem statement:** In Mexico, incidence of FN is of 62% of children with solid tumors treated with cisplatin-based chemotherapy (CBC). Cisplatin is one of the most nephrotoxic drugs being used in clinical setting. Nephrotoxicity is usually manifested by tubular damage that causes electrolyte losses, specially of magnesium. Recently, an association of hypomagnesemia and FN apparition. This association has a biologic explanation in the fact that magnesium is a necessary cofactor for the neutrophil's diapedesis and complement activation. To our knowledge, the role of magnesium supplementation in reducing FN episodes has not been explored. With this evidence in mind, we wondered if oral supplementation with magnesium will reduce FN episodes in pediatric oncology patients treated with CBC.

**Objective.** Determine the efficacy of oral supplementation with magnesium to reduce FN episodes in pediatric oncology patients treated with CBC.

**Hypothesis.** Previous clinical trials made in adult population had report that supplementation with magnesium salts reduce episodes of hypomagnesemia between 13 to 50%. Thus, oral supplementation with magnesium oxide will reduce in 20% FN episodes in pediatric oncology patients treated with CBC.

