### *Procedure*

Basal status of trial will be integrated at the moment the attending physician indicates that the patient will be treated with cisplatin-based chemotherapy (CBC). The clinical monitor will establish contact with the parent of the patient and explain the purpose of the trial and will invite them to participate through signing the informed consent. Once the informed consent is signed the clinical monitor will explain the patient the purpose of the trial in order to obtain the informed assent.

To prove the hypothesis, it is required to randomize 107 CBC cycles to the intervention group and 107 CBC cycles to the control group. To determine whether the patient will receive supplementation or not in that CBC cycle, the clinical monitor will notify the principal investigator that a patient will commence treatment. In response the investigator will communicate the clinical monitor where to allocate the patient's CBC cycle. Randomize will be made by generating non-repeated random numbers with the program available at: <http://randomnumbregenerator.intemodino.com/es/generador-de-numeros-aleatorios.html>.

Patients assigned to the supplementation group will receive institutional care protocol plus a bottle with magnesium oxide tablets and will be explained that they should take a tablet daily. In the case that the patients were assigned to the control group they will receive institutional care protocol only.

Oral supplementation with magnesium consists on a daily tablet (245 mg magnesium oxide and 5mg magnesium gluconate, GNC, US). Supplementation will be interrupted when the patients returns for the administration of another cisplatin cycle or with the appearance of a febrile neutropenia episode. In the same sense, patients on control group will be monitored until an FN episode appears or until they return for the next cisplatin cycle.

The main outcome of this study is the apparition of febrile neutropenia that is defined as a neutrophils total count below  $1000/\text{mm}^3$  together with a unique temperature  $>38.3\text{ }^\circ\text{C}$  or a sustained temperature of  $\geq 38\text{ }^\circ\text{C}$  for over an hour. Patients with a neutrophils total count  $<100/\text{mm}^3$  will be considerate as a profound neutropenia. Clinical monitor will visit the emergency department every day to identify if one of the enrolled patients has been hospitalized due febrile neutropenia diagnosis.

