## 7. Analysis data plan

Continuous variables with normal distribution will present as means and standard deviation. If variable have free distribution they will be presented as median and interquartile ranges. Categorical variables will be presented as frequencies and percentages. Operability of variables is showed at Appendix 3. Statistic differences at basal status will be calculated through t-Student test for continuous variables, whilst qualitative variables will be contrasted by  $\chi^2$  test. A  $p < 0.05$  will be considered as statistical significance.

Proportion of patients with febrile neutropenia will be calculated in both groups means the division of number of cases with febrile neutropenia between the total of CBC cycles assigned to each group (experimental or control). Efficacy of supplementation with magnesium will be determined through calculation of Relative Risks with Confidence Interval of 95% (CI 95%). Relative Risks will be considered significant when the value of CI95% don't cross the unit. Furthermore, Absolute Risk Reduction and Number Needed to Treat will be calculated. To adjust principal confounding variables, a Multivariate Analysis will be made with a Multiple Logistic Regression. Analysis by protocol (just patients that finish protocol) and by intention to treat (including all patients) will be made. Statistical analysis will be made performed with SPSS software v.21 (Chicago, IL, US).

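### Does the 62% control rate, worded as incidence in children but used per randomised cycle, undermine the stated 80% power?

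*Combined protocol and SAP*

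**What the plan says.** The Abstract states: "In Mexico, incidence of FN is of 62% of children with solid tumors treated with cisplatin-based chemotherapy (CBC"). The Background (Febrile Neutropenia) and the Problem statement repeat this, and the Background cites reference 17, the team's own cohort. None of these places gives an observation period or the number of cycles per child.

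The trial itself works by cycle:

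- **Allocation** (section 6, Procedure) is made "To determine whether the patient will receive supplementation or not in that CBC cycle".
- **Follow-up** (same section) ends within the cycle: "patients on control group will be monitored until an FN episode appears or until they return for the next cisplatin cycle".
- **Primary proportion** (section 7) is "the division of number of cases with febrile neutropenia between the total of CBC cycles assigned to each group".
- **Sample size**: "it is required to randomize 214 cycles and assign 107 to control group and 107 to supplemented group". The assumption is that the "non-exposed group will have a proportion of 62%, while supplemented group will have a proportion of 42" per cent, described as a delta of 20%, with two-sided alpha 0.05, beta 0.20 and a continuity correction. References 17 and 35 are cited.

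The wording is not consistent about the unit. Section 7 introduces its cases-per-cycle ratio with "Proportion of patients with febrile neutropenia will be calculated in both groups". The sample size paragraph opens with "Necessary number of patients was estimated considering a normal distribution means two proportions formula" and closes with a number of cycles.

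**The concern.** A child treated over several cycles has several chances of FN. The proportion of children who ever have an episode is then higher than the risk in any one cycle. If the 62% is of that kind, it overstates the control risk for a trial that counts cycles. A lower control risk with the same proportional benefit leaves a smaller absolute difference, and 214 cycles would have less than the stated 80% power. A null result could then be taken as stronger evidence against magnesium than the design can give.

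The supplemented rate invites the same doubt. Reference 35 is described in the Background as an adult trial of hypomagnesemia, so it supplies no FN risk per cycle.

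**Working it through.** **Inputs** (Sample Size Calculation): p1 = 0.62, p2 = 0.42, d = 0.20, two-sided alpha 0.05 (z = 1.960), power 0.80 (z = 0.842), allocation 1:1, continuity correction.

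**1. The plan's own figure.** With the mean proportion p̄ = 0.52:

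n = [1.960·√(2·0.52·0.48) + 0.842·√(0.62·0.38 + 0.42·0.58)]² / 0.20² = 96.8

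n corrected = (n/4)·[1 + √(1 + 4/(n·d))]² = 106.5, so 107 per arm. This matches the plan.

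Inverting the correction gives the effective size n′ = (107 − 1/d)²/107 = (107 − 5)²/107 = 97.2, and power 80.2%.

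**2. Lower control risk at 107 per arm.** The left-hand power column keeps the plan's 20-point difference. The right-hand one keeps the implied risk ratio (RR), 0.42/0.62 = 0.677.

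| Control risk per cycle | Power, 20 points kept | Power, RR 0.677 kept |
|---|---|---|
| 62% | 80.2% | 80.2% |
| 60% | 80.1% | 77.3% |
| 55% | 80.5% | 69.6% |
| 50% | 81.7% | 61.6% |
| 40% | 86.6% | 45.7% |

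**3. A cumulative reading.** The documents give no cycle count, so k = 2, 3 or 4 cycles per child is an assumption. With independent cycles and the same risk in every child, the per-cycle risk is 1 − (1 − 0.62)^(1/k).

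| k | Control risk per cycle | Power, 20 points kept | Power, 62% and 42% both cumulative | Power, RR 0.677 kept |
|---|---|---|---|---|
| 2 | 38.4% | 87.8% | 57% | 43% |
| 3 | 27.6% | 96.1% | 42% | 28% |
| 4 | 21.5% | 99.4% | 33% | 21% |

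The choice of effect scale alone moves power at k = 2 from 43% to 88%.

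**4. These per-cycle risks are lower bounds.** If risk p differs between children, Jensen's inequality gives E[(1 − p)^k] ≥ (1 − E[p])^k. For a given k, a cumulative 62% therefore implies a mean per-cycle risk of at least 38%, 28% or 21%. The constant-RR powers are floors in the same sense. The plan does expect children to differ: Appendix 2 records previous FN episodes and G-CSF use, and the Background reports a relative risk of 8.20 for hypomagnesemia.

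**5. Detectable difference.** At 80% corrected power with 107 per arm, the detectable supplemented risk is 0.304 for a 50% control risk, and 0.201, 0.115 and 0.072 for k = 2, 3 and 4. The differences are about 20, 18, 16 and 14 points. In absolute terms the design resolves 20 points or slightly better across the whole range.

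All figures treat cycles as independent, as the plan's formula does. Correlation between cycles of the same child is a separate question.

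**The case for a change.** The strongest reply is that holding 20 points is unrealistic when the base rate is low. It needs a relative reduction of 0.20/0.384 = 52%, 0.20/0.276 = 73% or 0.20/0.215 = 93% for k = 2, 3 or 4, against 0.20/0.62 = 32% at the planned rates. The Background offers little to support effects of that size: the only FN evidence it cites is a tendency of about 15% in adults. Section 7 judges efficacy by the relative risk, so a proportional effect is a natural assumption. The documents also show that children receive repeated cycles: tests are scheduled before each one, and Appendix 2 asks how many have been given. A per-child rate and a per-cycle rate can therefore differ.

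Part of this stands. The source's counting unit and observation window are not stated, and if the 62% is cumulative and the benefit proportional, power is below 80%. But both conditions are suppositions. Only reference 17 can settle the unit, and these authors call a cases-per-cycle ratio a proportion of patients, so their 62% of children may already be per cycle. The plan names no target relative risk: 0.677 is a quotient of its two rates, and section 7 also reports absolute risk reduction and number needed to treat.

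**Conclusion.** The concern does not hold as a fault in the plan. The sample size is arithmetically correct for the stated rates (107 per arm, 80.2% power). It is not true that 80% power requires the 62% to be a per-cycle figure: for the difference the plan names, power is between 80.1% and 99.4% at every lower control risk examined. The low values (62% at a 50% control risk, or 43%, 28% and 21% for two, three and four cycles) need a constant RR that the plan does not state. The last three also need an assumed cycle count and equal risk in all children.

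What remains is a missing description of where the 62% comes from, which the authors can supply from their own cohort when they report. It alters neither the 214 cycles nor the randomisation nor the analysis. A null result can be read from the 95% confidence interval of the relative risk and from the absolute risk reduction, whatever planning rate was used. No change to the plan follows.
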